7.4.7 Time to First Use of Rescue Medication

The time to first rescue will be measured from Time 0 (time of completion of study drug administration). If a subject does not take rescue medication but prematurely discontinues from the study or discontinues from the efficacy portion of the study, then for analysis purposes the subject's observation time will be the time of the discontinuation. For subjects who discontinue from the efficacy portion of the study, the discontinuation time will be considered to be a rescue event. The time will be considered to be a rescue event if the discontinuation from the study was due to lack of efficacy, otherwise, it will be considered a censored observation.

The distributions of time to first rescue in each treatment group will be presented graphically using Kaplan-Meier plots.

If data warrant, a summary table will present the number of subjects receiving rescue medication, number of censored subjects, median time to first dose of rescue, and 95% confidence intervals of the medians by dose cohort. Individual times to event will be listed.

7.4.8 Percent of Subjects Taking Rescue / Use of Rescue Medication over Time

Subjects will be counted as having taken rescue on any particular day based on the rescue medication page of the eCRF and the at home rescue diary. If additional medications, other than the study rescue medications, appear on the concomitant medications page and can be identified as having been taken for bunion pain, those medications will also be counted.

The proportion of subjects taking rescue will be summarized for each study day through Day 15. For summaries, subjects who discontinued from the efficacy portion of the study will be counted two ways. First, all medications on days up to and including the date of the discontinuation from efficacy will be included, but medications that were continued after the date of discontinuation from efficacy will not be counted. In a second analysis, all the medication for these subjects will be counted, regardless of whether it was taken before or after the subject discontinued from the efficacy portion.

In addition, the proportion of subjects taking any rescue medication during the following periods: 0 to 48 hours, 0 to 72 hours, 0 to 96 hours, Days 1 to 8, Days 3-8, and Days 9-15 and overall will be summarized and will be analyzed using Fisher's exact tests.

Separate summaries for opioid and non-opioid rescue use will be presented if sufficient data are present in the groups.

8 SAFETY EVALUATION

8.1 Overview of Safety Analysis Methods

All safety outcomes will be summarized using the safety population. Safety outcomes include:

- Incidence of TEAEs
- Clinical laboratory test results

- Vital sign measurements
- Electrocardiogram (ECG) results
- Physical Exam findings
- Surgical Site assessment findings
- Neurosensory Exam results

8.2 Adverse Events

Any untoward medical event that occurs after signing the ICF is considered to be an adverse event (AE). Treatment-emergent AEs are defined as AEs that start or worsen in severity after the first exposure to study drug and up to Day 29 for non-SAEs (up to Day 59 for SAEs). Verbatim terms used by investigators to identify AEs in the CRFs will be mapped to the appropriate preferred term (PT) and system organ class (SOC) using a standardized coding dictionary (MedDRA Version 19.1). All coding will be reviewed prior to database lock. All recorded AEs will be listed, but only TEAEs will be summarized.

For evaluation of causal relatedness to treatment, the categories are probably related, possibly related or unlikely related. For categorization in the summary tables, AEs designated as probably or possibly related will be considered to be related.

For the evaluation of event severity terms, the criteria are mild, moderate, severe or life-threatening.

In addition to a listing of all TEAEs, treatment related TEAEs, serious TEAEs, Deaths, and TEAEs leading to premature discontinuation from the study will be provided.

An overall summary will be prepared giving for each treatment group and overall both the number of TEAEs, and the number of subjects with TEAEs, as well as SAEs, treatment related TEAEs and TEAEs leading to premature discontinuation from study.

The number of subjects with AEs will be summarized for each treatment group by SOC and PT sorted in alphabetically by system organ class (SOC), and then by preferred term (PT) within SOC. These summaries will be given by treatment in separate tables for each of the following TEAE event sets:

- All events
- Treatment related events
- Serious events
- Events leading to premature discontinuation from study
- Events by maximum severity

If a given subject experiences a TEAE that maps to the same PT/SOC more than once, the subject will be counted only once for the SOC/PT at the greatest severity (i.e., mild, moderate, or severe) and causality (i.e., attribution to study material).

Duration of a TEAE lasting more than 24 hours will be computed in days as the stop date of the event minus the start date plus 1 and will be reported in days. TEAEs lasting less than 24 hours will be computed as stop date/time minus start date/time. If reported as ongoing at the time of database lock, the stop date is defined as the date of the last visit or the last date of any event for the subject in the database, whichever is later. If a TEAE is considered resolved, but the stop date is missing, the last day of the month will be imputed if the month and year are available. If only the year is available, and the year is the same as the year of the last visit, the stop date will be the latest of the last visit date or latest event for the subject in the database. If the year of the event is prior to the year of the last treatment, the end day and month will be set to 31 December.

For missing or partial start and stop dates/times, the most conservative imputation will be used (AEs will be assumed to be temporally related to the study medication). Table 8-1 will be used to impute any missing dates/times:

Table 8-1 Table of Imputation Rules for Missing AE Start Dates

| Missing Date Portion | Prior to Treatment | Same as Treatment Start Date | After Treatment Start Date |
|---|---|--|---|
| Day | 
Month and Year < Month and Year of Study treatment:
 
Start Day = 1
 
Stop Day=last day of the month
 | 
Month and Year = Month and Year of Study treatment:
 
Start Day = Day of first treatment
 
Stop Day= last day of the month
 | 
Month and Year > Month and Year of Study Treatment:
 
Start Day = 1
 
Stop Day=last day of the month
 |
| Day and Month Define Day as above, then: | 
Year < Year of first treatment:
 
Start Month = July
 
Stop Month = Dec
 | 
Year = Year of study treatment:
 
Start Month = Month of study treatment
 
Stop Month = Dec
 | 
Year > Year of study treatment:
 
Start Month = January
 
Stop Month = Dec
 |
| Day, Month, and Year | 
To be conservative, completely missing start dates will be imputed using the date of study treatment. Missing end dates will be imputed using date of last study contact with the subject
 | | |
| Time | 
Missing start times will be imputed as 00:01
 
Missing stop times will be imputed as 11:59
 | | |

After following these imputation rules, if the start date/time is imputed as a date after the end date/time, the start date/time will be set to the end date/time to provide a positive duration for the event incidence.

Missing assessments for AE study medication relationship or severity will be analyzed as related or severe respectively. No other imputation is planned for safety data.

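### SAP Table 8-1 sets a missing AE start time to 00:01 even on the treatment date, so an untimed Day 1 event falls before dosing and drops out of the TEAE tables

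*SAP*

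**What the plan says.** All the operative rules are in SAP 8.2.

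- **Definition.** "Treatment-emergent AEs are defined as AEs that start or worsen in severity after the first exposure to study drug". The window runs to Day 29, or to Day 59 for serious events.
- **Use.** "All recorded AEs will be listed, but only TEAEs will be summarized".
- **Stated principle for missing dates and times.** "the most conservative imputation will be used (AEs will be assumed to be temporally related to the study medication").
- **Date imputation (Table 8-1).** If the day is missing and the month and year match treatment, "Start Day = Day of first treatment". If everything is missing, "completely missing start dates will be imputed using the date of study treatment".
- **Time imputation (Table 8-1, Time row).** "Missing start times will be imputed as 00:01" and "Missing stop times will be imputed as 11:59". One rule covers every column of the table.
- **Correction below the table.** If imputation puts the start after the end, the start is moved to the end. Dosing time is not mentioned.
- **Duration.** "TEAEs lasting less than 24 hours will be computed as stop date/time minus start date/time".

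Protocol 13.4.6.1 defines treatment emergence by date: a non-serious or serious AE with onset on the day of treatment counts. Protocol 7.1.5 has non-serious AEs documented from study drug administration onward, and treats earlier ones as medical history.

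**The concern.** The Time row undoes the safeguard in the rows above it. Those rows move an undated event to the treatment date so that it will count as treatment-emergent. The Time row then puts an event with no time at one minute past midnight, before the subject was dosed. The SAP definition requires onset or worsening after exposure, so such an event is excluded from every TEAE summary.

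Incidence and severity of AEs is one of the two primary safety endpoints in the protocol synopsis. The rule acts on Day 1, and protocol 5.1.2 says that TRPV1 activation immediately produces hyperalgesia, erythema and local burning. Any error is an undercount, which is the non-conservative direction for a first-in-human safety study. SAP 5.2 also assigns events before the procedure to medical history, so a falsely early onset could be reclassified as well as left out of the tables.

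The imputed stop time raises a lesser problem. 11:59 is midday, so a same-day event that began in the afternoon would end before it started.

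**Working it through.** **Inputs**

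- Imputed start time 00:01 and imputed stop time 11:59, any date (SAP Table 8-1).
- SAP test: start later than first exposure (SAP 8.2). Protocol test: onset date on or after the treatment date (protocol 13.4.6.1).
- Order of Day 1: enrollment, randomization and baseline evaluations, then surgery with dosing before wound closure (protocol synopsis, Visit Schedule). No clock time is given, so dosing was assumed to start at 06:00, 08:00, 12:00 or 18:00.
- Six active and two placebo subjects per cohort, up to five cohorts, placebo pooled, and a combined active group shown (SAP 2.2 and 3).

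**Step 1: classify AEs that have no start time**

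| AE record | Imputed start | TEAE by SAP (date and time) | TEAE by protocol (date) |
|---|---|---|---|
| Dated Day 1 | Day 1, 00:01 | No, at all four dosing times | Yes |
| Day missing, treatment month | Day 1, 00:01 | No, at all four | Yes |
| Start date wholly missing | Day 1, 00:01 | No, at all four | Yes |
| Dated Day 2 | Day 2, 00:01 | Yes, at all four | Yes |

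The failure is confined to the treatment date. It holds whenever dosing starts after 00:01, so the choice among the four times does not matter. Only a recorded worsening after dosing rescues the event.

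**Step 2: does the correction below the table help?** It acts only when the start is later than the end. With both times missing on Day 1, 00:01 is earlier than 11:59, so it is not triggered.

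**Step 3: tables affected.** SAP 14.1.1 lists 18 tables numbered 14.3.x. Seven are TEAE tables (14.3.1.1 to 14.3.1.7). The other 11 are unaffected: 6 laboratory, 1 vital signs, 1 surgical site, 2 neurosensory and 1 ECG (6 + 1 + 1 + 2 + 1 = 11).

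**Step 4: size per lost subject.** The fall in incidence is 100 × k / n points, where k is the number of subjects whose only TEAE in a table row is lost. All five cohorts are assumed full.

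| Group | n | k = 0 | k = 1 | k = 2 |
|---|---|---|---|---|
| One dose group | 6 | 0 | 16.7 | 33.3 |
| Pooled placebo | 5 × 2 = 10 | 0 | 10.0 | 20.0 |
| Combined active | 5 × 6 = 30 | 0 | 3.3 | 6.7 |

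The documents do not allow k to be estimated. Hour-based durations in SAP 8.2 presuppose that times are collected, and Day 1 is inpatient. However, the AE items listed in protocol 11.1.2 include an onset date and no onset time.

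**Step 5: stop time.** For a recorded start of 14:00 and a missing stop time on the same day, 11:59 − 14:00 = −2 h 01 min. With 23:59 it is +9 h 59 min. The correction below the table is worded for an imputed start, so it does not clearly apply here. No planned table reports duration, so only listed durations are affected.

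**Step 6: check of the fix.** Set the missing start time on the treatment date to Time 0, assumed 10 minutes after dosing starts. The untimed Day 1 event becomes a TEAE at all four dosing times, and Day 2 events do not change. The stop-time edit must go with it. With dosing at 12:00 and both times missing on Day 1, the start becomes 12:10 while the stop stays at 11:59. The correction then moves the start back to 11:59, before dosing. With a 23:59 stop, 12:10 is earlier than 23:59 and the start is left alone.

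**The case against.** The strongest reply is that the SAP never says treatment emergence is derived by comparing imputed clock times with dosing time. A programmer could compare dates only, or follow the lead-in about temporal relation, and then no event would be lost. It is true that the defect would not arise on that reading. But the SAP does not state that reading. A definition that turns on what happens after exposure, together with an explicit rule for missing times, points to a date-and-time comparison. Following the lead-in would mean overriding the only operative row.

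Second, the protocol's collection rule governs what is recorded, not how TEAEs are classified. It also means that a non-serious AE on the AE page should already be post-dose, so a 00:01 onset would look odd on review. That is fair as mitigation, but it does not change the derived flag.

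Third, the frequency is unknown and the point changes are large mainly because the groups are small. This stands. They show the effect per subject lost and are not an estimate of impact.

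Fourth, the consequences are bounded. Dosing is under anesthesia with a bupivacaine block. Pain, surgical site and neurosensory findings are captured separately. Stopping rules and DMC review do not rest on the final TEAE flag, no formal safety comparisons are planned, and all AEs stay in the listings. All of this stands, and it limits the point to the final AE summaries.

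**Conclusion.** The concern holds. As written, Table 8-1 gives an untimed AE on the treatment date, or imputed to it, a pre-dose onset, and SAP 8.2 then keeps it out of all seven TEAE tables. This contradicts the SAP's own lead-in and the date-based rule in protocol 13.4.6.1.

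The direction is certain: an undercount of a primary safety endpoint on Day 1. The size is not known. It is zero if every Day 1 AE has a start time, and otherwise 16.7, 10 or 3.3 points per subject lost from a row in a dose group, pooled placebo or combined active.

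The conclusion assumes that TEAE status is derived on date and time, that dosing starts after 00:01, and that no later worsening is recorded. The percentages also assume five full cohorts. The 11:59 stop time is a separate and smaller fault that affects listed durations only. Both should be corrected before database lock.

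**What to change.** Amend the Time row of SAP Table 8-1 in two places, together:

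1. **Start time.** When the start date is, or is imputed to, the treatment date and the time is missing, impute the start as just after the start of study drug administration. Use Time 0 if only completion of dosing is recorded. Make an exception where a recorded stop date/time or another record shows that the event was pre-dose. Keep 00:01 for all other dates.
2. **Stop time.** Replace 11:59 with 23:59, capped at last contact with the subject.

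In place of the start-time edit, not in addition to it, the SAP could restore the date-based TEAE rule of protocol 13.4.6.1. That is a broader change. It would also count a documented pre-dose SAE on Day 1, and it would bring in an increase in relationship as a trigger. The time-imputation edit is therefore the narrower repair.

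The cost is two lines of SAP text and the matching derivation code before database lock, with no new data collection.

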- Physical exam: 1, 24, and 48 hours after the administration of study medication.
- ECG: 1.5 hours after the administration of study medication.
- Surgical Site assessment: 24 and 48 hours after the administration of study medication.
- Neurosensory Exam of the Foot / Great toe (bilateral): 24 and 48 hours after the administration of study medication.
- Clinical laboratory tests (chemistry/coagulation, hematology, and urinalysis): 1.5 hours after the administration of study medication.
- Blood draw for PK analysis: are at baseline (before dosing), and at 5 minutes, 15 minutes, 30 minutes, 45 minutes, and 1, 1.5, 2, 2.5, 3, 3.5, 4, 6, 8, 12, 16, 24, 36, and 48 hours after dosing.

Subjects with inadequately controlled pain may request rescue at any time. However, subjects will be encouraged to receive rescue medication only with an NPRS ≥ 4 . Additionally, subjects should be encouraged to wait at least 1 hour after completion of surgery (i.e. completion of sutures) before utilizing pain rescue medication, if possible. Pain intensity (NPRS) will be completed within 15 minutes prior to use of pain rescue medication. While in-clinic, subjects will be treated with the prescribed analgesic regimen (oxycodone 5 mg every 2 hours); however, if subjects do not get adequate analgesic relief they will be discontinued from the efficacy portion of the study. At this point, subjects will receive standard of care analgesics (which may or may not include intravenous opioids). Regardless of discontinuation status, subjects will be followed for safety. Discontinuation affects the computation of the analgesic endpoint only. From Day 3 to 15, over-the-counter standard of care analgesics may be used for management of pain. If needed for management of NPRS score of 4 or higher, oxycodone 5 - 15 mg every 4 - 6 hours.

After completing the assessments through 48 hours after study medication administration, the diary for at-home use will be reviewed and subjects will be discharged from the study center with the diary to record pain assessments and pain medication at home. Subjects will be provided routine standard of care for pain management after discharge from the study center. In their diary, subjects will assess their pain intensity once in the morning (08:00 ± 4 hours), and once in the evening (20:00 ± 4 hours) using the NPRS. Subjects will also record any medication they take to

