- Change from baseline is defined as post-baseline value minus baseline value.
- Duration of an AE will be computed in days for AEs lasting longer than 24 hours, and as hours for AEs lasting less than 24 hours. Duration in hours will be calculated as the stop date/time of the event minus the start date/time. Duration in days will be calculated by using stop date minus the start date +1 if AE occur on or after taking study medication. If AE occur prior to the study medication, then the duration will be calculated by using stop date minus the start date; If reported as ongoing at the time of database lock, the duration will be calculated using the date of the last visit or the last date of any AE for the subject in the database, whichever is later. Missing dates will be imputed as described in Table 8-1.
- The number of days in the study is computed as: [Date of study completion or withdrawal minus the date of study drug administration (Day 1)] + 1.
- If duplicate values are obtained at a given visit (e.g., repeated vital sign measurements), the last value will be used unless it is noted that the measurement was in error for that value. Values that compromise interpretation will not be used in summaries (e.g., values that were obtained post-dose will not be summarized as pre-dose values).
- If a pre-rescue NPRS is recorded in the same minute as a rescue medication is recorded, the NPRS will be assumed to have occurred PRIOR to the administration of rescue.
- If a subject experiences inadequate analgesic relief and are discontinued from the efficacy portion of the study the date/time of the discontinuation will be assumed to be the date/time of the start of standard of care analgesic rescue.

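### SAP Table 8-1 imputes a missing AE stop time as midday, giving a negative or zero duration for same-day AEs with a recorded afternoon onset; year-only stop dates also have two conflicting rules

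*SAP*

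**What the plan says.** The time row of SAP Table 8-1 (section 8.2) has two rules: "Missing start times will be imputed as 00:01" and "Missing stop times will be imputed as 11:59". Section 8.2 introduces the table with "For missing or partial start and stop dates/times, the most conservative imputation will be used", and explains in parentheses that AEs are to be taken as temporally related to study drug.

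Duration depends on these times only for short events. SAP section 3 states "Duration in hours will be calculated as the stop date/time of the event minus the start date/time", and section 8.2 repeats it: "TEAEs lasting less than 24 hours will be computed as stop date/time minus start date/time". For events over 24 hours both sections use calendar dates (for on-treatment events, stop date minus start date plus 1).

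A repair sentence follows the table. If a start is imputed after the end, "the start date/time will be set to the end date/time to provide a positive duration for the event incidence".

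For a resolved TEAE with only the year of the stop date known, and that year equal to the year of the last visit, the text of section 8.2 says "the stop date will be the latest of the last visit date or latest event for the subject in the database". For a year equal to the treatment year, Table 8-1 sets the stop month to December, with the day set to the last of the month.

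**The concern.** The start time 00:01 can only be a 24-hour time, and the SAP uses that clock elsewhere, for example "once in the evening (20:00 ± 4 hours) using the NPRS" in section 2.2. The protocol's Appendix A form also asks for 24-hour times. So 11:59 is late morning. The other stop rules in Table 8-1 take the end of the interval (last day of the month, December) or the last study contact. Only the stop time falls in the middle of its interval.

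A stop fixed at midday can fall before a recorded onset on the same date, and a programmer following the rule then gets an impossible duration. AE duration is a derived variable in this first-in-human safety study, and the repair sentence does not clearly resolve the problem. The year-only conflict is a separate instruction that cannot be programmed as written, because two rules cover the same case.

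**Working it through.** The plan gives no derived figure to reproduce, so the check applies its own rules to example events.

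**Inputs.** Imputed start 00:01 and imputed stop 11:59 (SAP Table 8-1). Under 24 h: duration = stop date/time - start date/time. Over 24 h: duration = stop date - start date + 1 (SAP sections 3 and 8.2). The comparison value is 23:59, the last minute of the day. The onset times are illustrative.

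| Onset | Stop date, time missing | With 11:59 | With 23:59 |
|---|---|---|---|
| 14:00 | same day | 11:59 - 14:00 = -2 h 01 min | 23:59 - 14:00 = 9 h 59 min |
| 08:00 | same day | 3 h 59 min | 15 h 59 min |
| missing (00:01) | same day | 11 h 58 min | 23 h 58 min |
| 14:00 | next day | 21 h 59 min, reported in hours | 33 h 59 min, reported as 2 days |
| 08:00 | next day | 27 h 59 min, reported as 2 days | 39 h 59 min, reported as 2 days |
| 14:00 on Day 1 | Day 4 | 69 h 59 min, reported as 4 days | 81 h 59 min, reported as 4 days |

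The pattern follows from the arithmetic:

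- Same-day stop, onset after 11:59: negative.
- Same-day stop, onset before 11:59: 12 h shorter than with 23:59.
- Next-day stop, onset after 11:59: under 24 h as written, so reported in hours instead of as 2 days.
- Over 24 h under both rules: no change, because only dates are counted.

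**The repair sentence.** It can be read in two ways.

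- Literally, it acts only when the start was imputed. A recorded 14:00 onset is outside it, and -2 h 01 min stands.
- Broadly, it acts whenever start exceeds end. The recorded 14:00 becomes 11:59 and the duration is 11:59 - 11:59 = 0 h, which is not the positive value the sentence promises. On Day 1, if dosing was later than 11:59 (an assumption; the documents give no dosing times), the event then appears to start before study drug. SAP section 8.2 requires a TEAE to start or worsen after first exposure and summarizes only TEAEs.

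**Year-only stop date.** Assume dosing on 1 March 2018, Day 29 on 29 March as the last visit, no later event, and a stop date recorded only as 2018. The text of section 8.2 gives 29 March 2018. Table 8-1 gives 31 December 2018. The difference is 2 days left in March + 275 days from April to December = 277 days.

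**The case against.** The strongest reply is that this is a typing slip with almost no reach. The planned AE tables, 14.3.1.1 to 14.3.1.7, cover incidence, severity, relatedness and discontinuation. None reports duration, and no listing title mentions it. The protocol's list of AE data (section 11.1.2) names onset and resolution dates but no times. If times are not collected, a same-day AE always runs from 00:01 to 11:59 and is never negative. The documents give no rate of missing times, and subjects are observed on site for the first 48 hours. All of this stands and keeps the point minor. SAP sections 3 and 8.2 do, however, compute durations from date/times, so the plan expects times to exist.

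Several stronger readings are tempting, and the documents do not support them.

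- A reader might infer that every AE with a missing stop time is 12 h too short. The 12 h is the gap to 23:59, not to the unknown true stop. An event from 08:00 to a true 09:30 is already too long under 11:59. Events over 24 h under both rules do not change.
- A reader might infer that the rule contradicts the promise of conservative imputation. Section 8.2 explains that promise as temporal relation to study drug, not length of the event.
- A reader might add the negative durations to the possible loss of TEAE status. For any one event these belong to opposite readings of the repair sentence and cannot both occur.
- A reader might take loss of TEAE status as likely. It needs a same-day stop with no stop time, dosing after 11:59, an onset later still, and the broad reading. Protocol section 13.4.6.1 counts onset on the date of treatment, so only the SAP wording leaves this gap.

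It is also fair to say that 23:59 is no more accurate for a given event: an AE from 14:00 to a true 08:00 next day (18 h) would be reported as 2 days. The case for 23:59 is that it cannot precede a recorded onset on the same date and that it matches the table's other stop rules.

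**Conclusion.** The point holds and is minor. For a recorded onset after 11:59, a stop on the same date and a missing stop time, the SAP gives a negative duration on the literal reading of the repair sentence, or 0 h with an overwritten onset on the broad reading. Neither is usable. Other AEs reported in hours are 12 h shorter than under an end-of-day rule, and next-day stops after an afternoon onset change unit. The year-only conflict is also real, but limited to cases where the treatment year is also the year of the last visit; the 277 days is an illustration on an assumed dosing date.

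The effect is confined to derived durations in the datasets or listings, any statement on duration in the CSR, and possibly TEAE status through the broad reading. How many AEs are affected cannot be estimated from the documents. The negative case rests on AE times being collected, with the onset time recorded and the stop time missing.

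**What to change.** Before database lock, make three edits to SAP section 8.2:

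1. In Table 8-1, change the imputed stop time from 11:59 to 23:59, no later than the last study contact.
2. In the sentence below the table, state that it adjusts only imputed values and never a recorded start.
3. In Table 8-1, for a year-only stop date in the treatment year, replace the December stop month with the rule in the text (the later of the last visit and the latest event).

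The cost is a few words and the matching lines of the dataset specification. No new data or subjects are needed, and no planned table changes its layout.
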